13.5.3.2.2 Sensitivity Analysis

Several sensitivity analyses will be implemented to explore robustness of missing value imputation methods for the analysis of HbF responder rate at Week 24:

1. For imputation rule #2 in Section 13.5.3.2.1, use HbF value from Week 12 when Week 24 and Week 16 are both missing, i.e. If HbF value is missing at Week 24, HbF value at Week 16 will be used for the analysis; If HbF value at Week 16 is also missing, HbF value at Week 12 will be used for the analysis; subject will be treated as a non-responder if HbF value is missing for Weeks 24, 16 and 12.
2. For imputation rule #2 in Section 13.5.3.2.1, If HbF value is missing at Week 24, HbF value at Week 16 will not be used for the analysis; i.e. Subject will be treated as a non-responder if HbF value is missing for Week 24.

3. The average value of HbF values at Week 24 and Week 16 will be used to determine if a subject is a responder/non-responder at Week 24. If one of them is missing, the other will be used for the analysis. If HbF value at Week 24 and Week 16 are both missing, the subject will be treated as a non-responder.

In addition, sensitivity analyses for HbF responder rate at Week 24 will be conducted using the mITT and PP analysis sets. Major protocol deviations and subjects (or data) excluded from the PP analysis set will be defined by the Sponsor in a blinded manner prior to database lock. No imputation will be performed for the PP analysis.

All sensitivity analyses above will be performed at FA.

13.5.3.3 Supplementary Analysis

Subgroup analysis will be performed for the key secondary efficacy endpoints and detailed in [Section 13.5.6](#). Other supplementary analysis may be added.

13.5.4 Other Secondary Endpoints

Proportion of VOC-free subjects

VOC-free subjects are defined as these who did not experience a VOC after the first dose of study drug through the end of treatment. Proportion of VOC-free subjects will be analyzed using a stratified Cochran-Mantel-Haenszel (CMH) test adjusted for stratification factors of region (North America/Europe vs. Africa/Middle East) and HU use (Yes vs. No) using the ITT analysis set. Sensitivity analysis will be performed for proportion of VOC-free subjects using the PP analysis set.

Annualized rate of VOC-related hospitalizations

Annualized rate of VOC-related hospitalization is calculated as total number of VOC-related hospitalizations / ([Date of last dose of study drug – date of first dose of study drug + 1] / 365.25).

VOC-related hospitalization will be determined from the “Adverse Event” CRF when the AE’s preferred term = “sickle cell anaemia with crisis” and “Did the adverse event result in initial or prolonged hospitalization for the subject?” = “Yes”. Date of last dose of study drug are collected from “End of Treatment” CRF page. If that date is not available (which is expected for some of the subjects in IA), the data cut-off date will be used.

VOC-related hospitalization-free subjects are defined as these who did not experience a VOC-related hospitalization after the first dose of study drug through the end of treatment.

Analyses of annualized rate of VOC-related hospitalizations will be done in the same way as in [Section 13.5.2](#) as for the primary endpoint (annualized rate of VOCs).

Annualized rate of days hospitalized for VOC-related hospitalizations

Annualized rate of days hospitalized for VOC-related hospitalizations is calculated as (sum of total number of days hospitalized for VOC-related hospitalization / ([Date of last dose of study drug – date of first dose of study drug + 1] / 365.25)).

Number of days hospitalized for VOC-related hospitalization is calculated as the sum of (Date of Discharge – Date of Admission + 1) for all AEs with preferred term = “sickle cell anaemia with crisis” and “Did the adverse event result in initial or prolonged hospitalization for the subject?” = “Yes”.

Date of last dose of study drug are collected from “End of Treatment” CRF page. If that date is not available (which is expected for some of the subjects in IA), the data cut-off date will be used.

Annualized rate of days hospitalized for VOC-related hospitalization will be analyzed in the same way as annualized rate of VOC-related hospitalization.

Time to first for VOC-related hospitalization

The time to first VOC-related hospitalization event will be analyzed using Kaplan-Meier methods. Time in months to the first VOC-related hospitalization event can be calculated as ([date of first VOC-related hospitalization event – date of first dose + 1] / 30.4375).

Time to second VOC

This analysis of time to second VOC event will be analyzed using Kaplan-Meier methods similar to the analysis of the time to first VOC. A patient with less than two VOCs before withdrawal or completion of the study is considered censored at the time of withdrawal or completion of the study.

A sensitivity analysis will be performed separately, excluding these subjects without any VOCs.

HbF responder rate (as defined by proportion of subjects with an absolute increase of $\geq 3\%$ in HbF from baseline) at Week 52

This analysis of HbF responder at Week 52 will be similar to the HbF responder rate analysis at Week 24 ([Section 13.5.3.2](#)). Similar imputation rules will apply:

1. Subject will be treated as a non-responder if there is an initiation of HU post randomization and prior to Week 52.
2. HbF value from Week 36 (the last scheduled visit before the target analysis visit) will be used when Week 52 value is missing,
3. Any HbF value within 8 weeks (56 days) of RBC transfusion is excluded from all analyses.

Change from baseline in HbF (%) and F-cells (%) at Week 24 and Week 52

Change and percentage change from baseline in HbF (%) and F-cells (%) will be analyzed using mixed models for repeated measures (MMRM) with baseline value as a covariate, fixed effects for region (North America/Europe vs. Africa/Middle East), HU use (yes vs. no), treatment, visit, and treatment-by-visit interaction. Unstructured covariance matrices will be assumed for all models, but auto-regressive 1 (AR1) and compound symmetry (CS) may also be assessed (in that order) if the unstructured covariance matrix does not converge.

Values used at the visit and change from baseline for each parameter will be summarized for each post-baseline timepoint. The LS Mean estimates and 95% CIs will be displayed for all treatment groups. LS Mean difference estimates and 95% CIs with p-values for all IMR-687 treatment groups (relative to placebo) will be provided.

Line plots will be provided for LS mean change from baseline +/- standard error (SE) at each post-baseline visit by treatment group.

Waterfall plots will be provided for change in HbF (%) from Baseline to Week 24 and from Baseline to Week 52 by treatment group, respectively. The plot of individual subjects change from baseline will be displayed with a reference line at 3%.

If the HbF value at Week 24 and Week 52 were imputed from the previous visits in the responder analysis, the imputed value will also be used for the MMRM, summary statistics and waterfall plots. The observed value and imputed value will both be presented in the data listing.

Hb responder rate (as defined by proportion of subjects with an absolute increase of ≥ 1.0 g/dL in total Hb from baseline) at Week 24 and Week 52

This analysis of Hb responder rate at Week 24 and Week 52 will be similar to the HbF responder rate analysis at Week 24 and 52. The same imputation rules will apply.

Change from baseline in total Hb (g/dL) at Week 24 and Week 52

The analysis of total Hb (g/dL) at Week 24 and Week 52 will be similar to Change (and percentage change) from baseline in HbF (%) at Week 24 and 52.

Change from baseline in biomarkers of RBC hemolysis (% and absolute reticulocytes, unconjugated [indirect] bilirubin, and LDH) at Week 24 and Week 52

The analysis of change (and percentage change) from baseline in biomarkers of RBC hemolysis at Week 24 and Week 52 will be similar to the analysis of other change from baseline efficacy variables. The analysis will be performed for each of the following parameters, at Week 24 and Week 52 separately:

- % Reticulocytes
- Absolute Reticulocytes
- Unconjugated [indirect] Bilirubin
- Lactate dehydrogenase (LDH)

Line plots will be provided for LS mean change +/- SE.

Change from baseline in each measured subdomain of the ASCQ-Me questionnaire at Week 24 and Week 52

The Adult Sickle Cell Quality of Life Measurement Information System (ASCQ-Me®) is a systemic, reliable, and valid method for documenting adult SCD patient-reported outcomes. The questions are grouped into 3 domains (physical, social, and emotional) encompassing 7 subdomains, of which the following 5 will be measured: emotional impact, pain impact, sleep impact, social functioning impact, and stiffness impact. Of note, pain episodes and frequency, and SCD medical history checklist will not be evaluated, but the reliability of the instrument should allow for use of only a subset of the validated domains. Each subdomain includes 5 to 9 items. Recall periods vary by subdomain and even question, with most of the periods being from 7 days to 30 days. Subdomain scores are standardized to have a mean of 50 and a standard deviation of 10.

Each of the five subdomains measured in this study consists of five questions. Responses to each question range in numeric value from 1 (Always/Very/Very much) to 5 (Never/Not at all). To calculate each subdomain score, responses to each of the 5 questions will be summed, and then converted to T-scores with standard errors (SE) based on the scales in [Appendix 1](#). If any question within a subdomain is not answered, the subdomain score will be missing for that subject/time point. Untransformed scores range from 5 to 25, and the range of converted scores depends on the subdomain. Higher scores indicate healthier status.

The analysis of change from baseline in each measured subdomain of the ASCQ-Me questionnaire at Week 24 and Week 52 will be based on an analysis of covariance (ANCOVA) model with fixed effects for treatment, visit, and treatment-by-visit interaction, and baseline value, region, and HU use as covariates. Mean (95% CI), Mean difference (95% CI), and p-value will be provided. The T-score analysis will be performed for each of the following parameters (subdomains), at Week 24 and Week 52 separately:

- Emotional Impact
- Pain Impact
- Sleep Impact
- Social Functioning Impact
- Stiffness Impact

Line plots will be provided for LS mean change +/- SE.

Change from baseline in total preference score and individual domain scores of the PROPr questionnaire at Week 24 and Week 52

The PROMIS-29+2 Profile (PROPr) questionnaire (version 2.1) consists of seven domain scores (Physical Function, Anxiety, Depression, Fatigue, Sleep Disturbance, Ability to Participate in Social Roles

and Activities, and Pain Interference), as well as a Cognitive Function short form and a Pain Intensity question. Each domain consists of four questions. Responses to each question range in numeric value from 1 (Unable to do/Never/Not at all/Very poor) to 5 (Without any difficulty/Always/Very much/Very good). The Cognitive Function short form consists of two questions where responses range from 1 (Not at all) to 5 (Very much). To calculate each domain score and cognitive function score, responses to each of the 4 questions (or 2 questions for the cognitive function) will be summed, and then converted to T-scores with SE based on the scales in [Appendix 2](#). If any question within a domain is not answered the domain score will be missing for that subject/time point. Untransformed scores range from 4 to 20, and the range of converted T-score depends on the domain. Higher scores indicate a healthier status.

The total preference (PROPs) score will be calculated using SAS codes provided in Appendix 1 of “The Development of a Preference-based Scoring System for PROMIS (PROPr): A Technical Report (v1.4)” by [Hanmer and Dewitt](#) (December 2017). The PROPs score is between 0 and 1 with higher scores indicating better quality of life.

The analysis of change from baseline in total preference score and individual domain T-scores of the PROPr questionnaire at Week 24 and Week 52 will be similar to the analysis of ASCQ-Me. The analysis will be performed for each of the following parameters, at Week 24 and Week 52 separately:

- Total Preference Score
- Physical Function
- Anxiety
- Depression
- Fatigue
- Sleep Disturbance
- Ability to Participate in Social Roles and Activities
- Pain Interference
- Cognitive Function
- Pain Intensity

Line plots will be provided for LS mean change +/- SE.

Change from baseline in overall score of the SCSES at Week 24 and Week 52

The Sickle Cell Self-Efficacy Scale (SCSES) is a 9-item QoL measure for adults with SCD. This measure is a self-appraisal of an SCD patient's ability to engage in daily functional activities and to manage SCD symptomatology. Response choices range from “not at all sure” to “very sure”. Responses from individual items are summed to give an overall score with higher scores indicating greater self-efficacy for coping with SCD. If the response for any of the individual questions is missing, the overall score will be missing.

The analysis of change from baseline in overall score of the SCSES at Week 24 and Week 52 will be similar to the analysis of ASCQ-Me. The analysis will be performed for Week 24 and Week 52 separately.

Line plots will be provided for LS mean change +/- SE.

Change from baseline in biomarkers of adhesion at Week 24 and Week 52

The analysis of change (and percentage change) from baseline in biomarkers of adhesion at Week 24 and Week 52 will be similar to the analysis of other change from baseline efficacy variables. The analysis will be repeated for each of the following parameters, at Week 24 and Week 52 separately:

- Soluble E-sel

- P-sel
- ICAM-1
- VCAM-1

Line plots will be provided for LS mean change +/- SE.

Change from baseline in biomarkers of inflammation at Week 24 and Week 52

The analysis of change (and percentage change) from baseline in biomarkers of inflammation at Week 24 and Week 52 will be similar to the analysis of other change from baseline efficacy variables. The analysis will be performed for each of the following parameters, at Week 24 and Week 52 separately:

- hsCRP
- MPO

Line plots will be provided for LS mean change +/- SE.

Change from baseline in biomarkers of cardiac stress at Week 24 and Week 52

The analysis of change (and percentage change) from baseline in biomarkers of cardiac stress at Week 24 and Week 52 will be similar to the analysis of other change from baseline efficacy variables. The following parameter will be analyzed at Week 24 and Week 52 separately:

- NT-proBNP

Line plots will be provided for LS mean change +/- SE.

Change from baseline in RBC indices at Week 24 and Week 52

The analysis of change (and percentage change) from baseline in RBC indices at Week 24 and Week 52 will be similar to the analysis of other change from baseline efficacy variables. The following parameter will be analyzed at Week 24 and Week 52 separately:

- MCV

Line plots will be provided for LS mean change +/- SE.

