8.5. Guidelines for Study Drug Dose Withholding or Discontinuation

In consultation with the medical monitor, the investigator may decide to withhold or discontinue study drug dosing in cases where tolerability or safety concerns emerge. [Table 2](#) provides recommended guidelines for these decisions.

If a study drug dosing is withheld due to an AE (Section [12](#)), subjects who continue on the study will have all assessments (except study drug administration) performed as per protocol.

If study drug dosing is discontinued for any reason, the specific circumstances surrounding the discontinuation must be recorded in the subject's eCRF. Any subject who discontinues study drug dosing must also be withdrawn from the study; however, all appropriate safety assessments and follow-up should be completed prior to withdrawal (Section [8.4](#)).

Table 2: Safety Guidelines for Study Drug Dose Reduction, Withholding, or Discontinuation

Dose Reduction	
Event	Recommended Action
A Grade 2 or higher TEAE that, in the opinion of the investigator, is both study drug related and that makes continued dosing at the current dose level inadvisable due to safety concern or lack of tolerability.	
Study drug may be reduced by 1 tablet for up to 14 continuous days.
 
If, in the opinion of the investigator, a longer dose reduction is clinically needed, the medical monitor should be contacted.
 
If, in the opinion of the investigator, the severity of the Grade ≥ 2 TEAE has reduced to Grade ≤ 1, the subject may resume study drug at the original dose. If the TEAE recurs after re-introduction of the original dose, the subject should be withdrawn from the study.

Dose Interruption (Hold)	
Event	Recommended Action
A Grade 3 or higher TEAE that, in the opinion of the investigator, is both study drug related and that makes continued dosing at the current dose level inadvisable due to safety concern or lack of tolerability.	
Study drug should be held for up to 7 continuous days until reduction in severity of the TEAE to Grade ≤ 2, then resumed at the original dose.
 
If, in the opinion of the investigator, dosing should be resumed at a lower dose, the medical monitor should be contacted.
 
If, in the opinion of the investigator, a longer dose hold is clinically needed, the medical monitor should be contacted or the subject should be withdrawn from the study.

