10.0 Conventions and Derivations

10.1 Method for Handling Missing Data

There will be no imputation of incomplete or missing data unless specified otherwise in this SAP.

Please refer to [Appendix 4](#) for specific data handling rules, including missing last dose date for IA, incomplete/missing dates for adverse events and prior/concomitant medications, interpretation of non-numeric results (e.g. “< BLQ”, “>x.xx”) from PK and laboratory measures, etc.

Efficacy and PK imputation for missing data will be detailed in [Section 13.5](#).

Imputation will be noted in the footnotes. The original values/results will be presented in the data listings.

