11.5 Modified Intent-to-Treat Analysis Set

The modified intent-to-treat (mITT) analysis set will include all randomized subjects who had at least 1 VOC in the 12 months prior to randomization and have received at least one dose of study drug. The mITT set will be used for sensitivity analyses of efficacy, PD, and clinical outcome parameters. Subjects will be analyzed according to their randomized treatment assignment.

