11.6 Per Protocol Analysis Set

The per protocol (PP) analysis set will include all subjects in the safety analysis set who had at least 1 VOC in the 12 months prior to randomization, completed at least 1 valid clinical outcomes assessment without major protocol deviations or events that would be expected to affect the analysis and did not discontinue prior to Week 24 for reasons other than AEs. Subjects will be analyzed according to the actual treatment they received. The PP set will be used for sensitivity analyses of efficacy, PD, and clinical outcome parameters.

Major protocol deviations and subjects (or data) excluded from the PP Analysis Set will be defined by the Sponsor in a blinded manner prior to database lock.

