13.5.2.3 Missing Value Consideration for the Primary Efficacy Analysis

The value of the primary endpoint, annualized rate of VOCs, will be non-missing by definition. However, subjects included in the ITT analysis may not all complete the 52-week treatment period. In the context of this endpoint, the unobserved VOC events after treatment discontinuation will be considered missing values. This calculation accounts for early treatment discontinuation by extrapolating the VOC rate annualized to one year. The primary analysis assumes the unobserved rate of VOC will be the same for the observed rate for the same subject.

Missing data will not be imputed for primary endpoint analysis methods. Data imputation strategies will be employed for sensitivity analysis.

Understanding the reasons why data are missing is important to correctly interpret and handle the observed data. If the missing data mechanism is independent of missing outcome values, conditional on earlier observed outcome variables and/or covariates, the outcome values are missing at random (MAR). If the probability of missingness depends on an outside variable not in the model or is related to unobserved outcome values at the time of dropout and possibly afterward then the values are missing not at random (MNAR).

Table 8 summarizes the classification with the potential reasons. The missing data pattern will be summarized and the impact of these missing values will be explored in the sensitivity analysis below.

Table 8 Classification of Missing Data Pattern

| Missing Data Pattern | Reason for Treatment Discontinuation |
|------------------------------|---|
| MNAR (Missing Not at Random) | 
Due to efficacy/safety related reasons:
 
 • Adverse Event • Death • Lack of Efficacy • Lost to Follow-up • Non-Compliance with Study Protocol • Non-Compliance with Study Drug • Physician Decision • Study Terminated by Sponsor • Subject Participation in Another Investigational Study • Trial Site Terminated by Sponsor • Withdrawal of Consent • Other (efficacy/safety related) |
| MAR (Missing at Random) | 
Due to non-efficacy/non-safety related reasons:
 
 • Pregnancy • Study Blind Intentionally or Accidentally Broken • Subject Erroneously Included in Study (i.e. did not meet eligibility criteria) • COVID-19 • Other (not efficacy/safety related) |

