13.5.3.1 Time to first VOC

The time to first VOC event will be analyzed using Kaplan-Meier methods. Time in months to the first VOC event can be calculated as $([\text{date of first VOC event} - \text{date of first dose} + 1] / 30.4375)$.

Both start and end date of VOC event will be collected from “VOC” CRF page. The start date of the VOC is not expected to be missing and will be used for the analysis. In the rare event the start date is missing, then the end date can be used. If both start date and end date are missing, no imputation will be made and the event will be excluded from the analysis.

Subjects who experience no VOC events during the study will be censored at their study end date (or date cut-off date if the study end date is not available). Using the ITT set, the number and percentage of subjects with events (subjects who experienced at least 1 VOC on-study) and censored (subjects who did not experience any VOCs on-study) will be presented. The 25th, 50th (median), and 75th percentiles, along

with associated 2-sided 95% CIs based on the Brookmeyer and Crowley method will be presented. The p-values from a stratified log rank test and hazard ratios (and 95% CIs) estimated from a stratified Cox regression model with treatment arm and stratification factors (region and HU use) as covariates will be presented for comparison of each treatment group to placebo. Kaplan-Meier curves will be produced for the time to first VOC with separate curves for each treatment group.

Sensitivity analysis will be performed for Time to first VOC using the mITT and PP analysis sets. Major protocol deviations and subjects (or data) excluded from the PP analysis set will be defined by the Sponsor in a blinded manner prior to database lock. No imputation will be performed for the PP analysis.

13.5.3.2 Other sensitivity analyses may be added. All sensitivity analyses will be performed at FA.HbF responder rate at Week 24

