13.5.3.2.1 Analysis and Imputation Methods

HbF responder rate (as defined by the proportion of subjects with an absolute increase of $\geq 3\%$ from baseline) at Week 24 will be assessed using a stratified Cochran-Mantel-Haenszel (CMH) test adjusted for stratification factors of region (North America/Europe vs. Africa/Middle East) and HU use (Yes vs. No). The ITT set will be used for this analysis.

The frequency and percentage of responders and non-responders at Week 24 will be presented for each treatment group as well as ORs, RRs, 95% Cis, and p-values from the CMH test comparing active groups to placebo.

Bar plots will be provided, and the proportion of subjects with response in HbF in each treatment group, Odds ratios, 95% CI, and p values will be displayed for each treatment comparison.

The following imputation rules will be applied for the key secondary efficacy endpoint (HbF responder at Week 24):

1. Subject will be treated as a non-responder if there is an initiation of HU post randomization and prior to Week 24.
2. If HbF value is missing at Week 24, the HbF value at Week 16 will be used for the analysis. If HbF value at Week 16 is also missing, subject will be treated as a non-responder.
3. Any HbF value within 8 weeks (56 days) of a RBC transfusion will be excluded from all analyses. If the subject does not have a valid HbF value at Week 24 and/or Week 16, subject will be treated as a non-responder.

Number of subjects with imputed values for the key secondary efficacy endpoint and the reason for imputation (imputed as non-responder because of initiation of HU post randomization, imputed with Week 16 value because of Week 24 value is missing, imputed from the last post-baseline assessment prior to RBC transfusion) will also be summarized. The observed and imputed Week 24 HbF values will both be summarized for the by-visit analysis.

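### The VOC-free proportion (step 4) has no fixed week and no rule for early leavers, so the reported percentage may not describe a VOC-free year; a cheap wording change fixes it

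*SAP*

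**What the plan says.** SAP 13.5.4 states that "VOC-free subjects are defined as these who did not experience a VOC after the first dose of study drug through the end of treatment". The proportion is compared by CMH test, stratified by region and HU use, in the ITT set. It is item 4 in the testing order of both SAP 12.3 (interim) and 12.4 (final). SAP Table 7 gives its time point as not applicable. The HbF and Hb responder rates in the same row carry Week 24 and Week 52 in their names.

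Three other provisions decide what happens to an early leaver:

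- Protocol 8.5: "Any subject who discontinues study drug dosing must also be withdrawn from the study". VOCs after that point are generally not observed.
- SAP 13.5.2.1 takes the last-dose date from each subject's End of Treatment CRF page.
- SAP 10.1: "There will be no imputation of incomplete or missing data unless specified otherwise in this SAP". None is specified for VOC-free status.

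The neighbouring endpoints do have a rule. For the primary rate, "the unobserved VOC events after treatment discontinuation will be considered missing values" (SAP 13.5.2.3). For time to first VOC, "Subjects who experience no VOC events during the study will be censored at their study end date" (SAP 13.5.3.1). For HbF response at Week 24, the Week 16 value is tried first, and then "If HbF value at Week 16 is also missing, subject will be treated as a non-responder" (SAP 13.5.3.2.1).

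**The concern.** Read literally, an ITT subject who stops at Week 4 without a VOC has had none through his or her own end of treatment, and so scores as a success. Short follow-up then raises the reported percentage, which a reader of the study report would take as the share of subjects with a VOC-free year. If dropout differs between arms, the stand-alone CMH test leans toward the arm that loses more subjects.

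The planned alternative analysis sets are only partial checks. The mITT set requires "at least 1 VOC in the 12 months prior to randomization and have received at least one dose of study drug", so it keeps every dosed early leaver. The PP set requires that subjects "did not discontinue prior to Week 24 for reasons other than AEs", so it keeps those who left for AEs and everyone who left after Week 24. The jump-to-reference, tipping-point and multiple-imputation analyses in SAP 13.5.2.4 are written for the annualized rate.

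**Working it through.** **Inputs from SAP 8.1.2 and Appendix 7.** 49 higher-dose and 31 placebo subjects; 3.0 and 5.0 VOCs per year (5.034 in the power program's input); SD 2.7; 25% dropout.

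**The plan's own figure.** Wilcoxon power for normal data, approximated by t-test power with each n multiplied by 3/π, is 0.876 (difference 2.0) or 0.886 (2.034) for 49 vs 31, against the stated 88%. For 37 vs 24 it is 0.775 or 0.788, against 78%. The planning values reproduce. The documents give no figure for the VOC-free proportion.

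**Assumptions added here.** Negative binomial counts matched to SD 2.7 at one year; dropout times uniform over 52 weeks and unrelated to VOC risk; T = 364/365.25 years.

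**Formulas.** With rate m and k = m²/(2.7² − m):

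- k = 9/4.29 = 2.1 for m = 3, and 25/2.29 = 10.9 for m = 5.
- Chance of no VOC by time t: P(t) = (k/(k + mt))^k.
- Mean of P over uniform dropout times: k/((k − 1)mT) × [1 − (k/(k + mT))^(k − 1)].

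| | Placebo, 5/yr | Active, 3/yr |
|---|---|---|
| No VOC by Week 4 | 68.6% | 80.4% |
| No VOC by Week 52 | 1.65% | 15.59% |
| Dropout counted VOC-free (mean) | 21.56% | 39.75% |

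**Reported percentage at 25% dropout in both arms, leavers counted as VOC-free.**

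- Placebo: 0.75 × 1.65 + 0.25 × 21.56 = 6.6%. Dropouts are 5.39/6.63 = 81% of those counted.
- Active: 0.75 × 15.59 + 0.25 × 39.75 = 21.6%. Dropouts are 9.94/21.63 = 46% of those counted.
- The difference between arms goes from about 14 to 15 points.

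**How far the count model matters.**

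- Common dispersion (k = 2.1 in both arms): placebo goes from 7.8% to 12.9%, with dropouts 55% of those counted.
- Poisson counts: placebo goes from 0.7% to 5.5%, active from 5.0% to 11.7%.

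**If event-free leavers count as not VOC-free.** Placebo is 0.75 × 1.65 = 1.2%; active is 0.75 × 15.59 = 11.7%.

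**Error of the stand-alone test with equal VOC rates.** Simulation of 40,000 trials per case, 49 vs 31, unstratified Mantel-Haenszel test, one-sided nominal 2.5%. Unequal dropout splits are assumptions.

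| Dropout active/placebo | Rule for leavers | Favours active (3/yr; 5/yr) | Favours placebo (3/yr; 5/yr) |
|---|---|---|---|
| 25/25 | VOC-free | 2.6%; 1.3% | 2.5%; 2.2% |
| 35/15 | VOC-free | 7.2%; 6.4% | 0.7%; 0.3% |
| 15/35 | VOC-free | 0.8%; 0.2% | 7.0%; 9.6% |
| 35/15 | Not VOC-free | 0.8%; 0.0% | 6.1%; 0.6% |

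With four equal strata, as a stand-in for the planned CMH test, the rate favouring active is 1–2% at 25/25, 3–4% at 30/20 and 6–7% at 35/15.

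**In sequence.** In 6,000 simulated null trials at 35/15, steps 1, 2 and 4 all favour active in about 1% or less, before the HbF step is counted.

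**The case against.** The strongest reply is that end of treatment is a defined time. Protocol 7.1.2 equates it with Week 52, and the protocol has a separate term, early termination, for leavers. On that reading the endpoint does have a week. SAP 10.1 does not settle the matter either: if VOCs after discontinuation are missing, as SAP 13.5.2.3 says for the primary endpoint, then not imputing them could leave VOC-free status missing. This stands in part. The schedule uses one shared ET/EOT visit and the CRF date is subject-specific, so the literal reading remains the more natural one. But a reader who infers that the SAP expressly scores early leavers as successes goes further than the text. Even with Week 52 understood, the plan does not say how to score someone who left at Week 4.

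A reader might also infer that step 4 threatens the trial's error control. The documents do not support that. SAP 12.4 and 13.5.7 allow a claim at step 4 only after the annualized rate, time to first VOC and HbF response have succeeded. Equal dropout does not inflate the error, and no dropout imbalance appears in either document.

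The contrast with HbF is also looser than it looks, because that endpoint is a visit-based laboratory value. It shows that the SAP states a rule elsewhere, not that the same rule belongs here. Finally, SAP 13.5.3.1 already plans Kaplan-Meier curves by treatment group in the ITT set with event-free leavers censored, so most of the remedy is in the plan.

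**Conclusion.** A minor point and a cheap improvement. The definition leaves early leavers unspecified, and its most natural reading counts an event-free leaver as VOC-free. At planning rates and 25% dropout this adds about 5 points on placebo and 6 on active. On placebo the starting value is only 1.6% (7.8% with a common dispersion), so a large part of the reported percentage would be dropouts.

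The direction follows from the definition. The size rests on the assumed count distribution and dropout timing, neither of which the documents give. The primary and key secondary endpoints are unaffected. The test leans toward one arm only if dropout is unequal, and steps 1–3 leave little confirmatory risk. What remains at stake is mainly the reported percentage, and a p-value that SAP 12.4 reports as nominal at the final analysis even if an earlier step fails.

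Separately, the SAP disagrees with itself on timing. Section 12.3 and Table 7 have step 4 tested at the interim, while Table 4 places the other secondary endpoints at the final analysis only.

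**What to change.** Before unblinding, amend SAP 13.5.4 to:

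1. Define VOC-free at Week 52, and at Week 24 if step 4 is tested at the interim.
2. Report the VOC-free percentage by arm at that time from the Kaplan-Meier analysis of time to first VOC already planned in SAP 13.5.3.1.
3. Keep the planned stratified CMH as the step-4 test.
4. Add one sensitivity CMH in which a subject who discontinued without a VOC counts as not VOC-free.

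Do not make step 4 depend on both CMH tests being significant. At 3 vs 5 per year and 25% dropout in both arms, that would cut its power from about 42% to 23%. In a fixed sequence, each failure there also makes every later step nominal.

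Separately, reconcile Table 4 with Section 12.3 and Table 7 on interim testing of step 4.

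The cost is SAP wording, one percentage read from a planned curve and one extra CMH run, with no new data. The downsides are lower reported percentages, reliance on non-informative censoring for the Kaplan-Meier estimate, and a sensitivity rule that penalises the arm with more dropout (6.1% null error against active at 35/15 and 3 per year).
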